7.3.2 GSRS score

GSRS is an interview-based rating scale consisting of 15 items for assessment of GI symptoms. Items are scored for intensity on a 7-grade Likert scale, defined by descriptive anchors such that 0 =none, 1 =minor, 2 =mild, 3 =moderate, 4 =moderately severe, 5 =severe, and 6 =very severe discomfort. The overall GSRS score is the mean of these 15 items, varying from 0 to 6; a score of 0 indicates that no symptoms are present, and a score of 6 indicates the worst possible degree of all symptoms. In addition, these 15 items can be grouped into 5 dimensions: abdominal pain syndrome (3 items, abdominal pain, hunger pain and nausea), reflux syndrome (2 items, heartburn and acid regurgitation), indigestion syndrome (4 items, abdominal distension, increased flatulence, borborygmus and eructation), diarrhea syndrome (3 items, constipation, hard stools and urgency of defecation) and constipation syndrome (3 items, constipation, hard stools and

feeling of incomplete evacuation). A dimension score is calculated as the mean of the items belonging to the specific syndrome. The primary analysis will be based on the overall GSRS score and sensitivity analysis will be based on the 5 dimension score as appropriate.

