4.4. Gastrointestinal Symptom Rating Scale

The GSRS is a weekly recall scale that has been modified for daily recall in this study.

The 7 severities of each of the 15 questions of the GSRS have a number assigned and will be summarized for a GSRS score as follows:

- no discomfort at all = 0
- minor discomfort = 1
- mild discomfort = 2
- moderate discomfort = 3
- moderately severe discomfort = 4
- severe discomfort = 5
- very severe discomfort = 6

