7.2.4. DMF-GI Monitoring Period

The duration of the DMF-GI Monitoring Period will be up to 28 days. On the first full day after the Randomization Visit, subjects will start taking DMF per the prescribing instruction. Subjects

CONFIDENTIAL

will make daily entries in the eDiary, recording pertinent information regarding GI-related events to allow the characterization of events that occur while taking DMF. During this period, if a subject meets the threshold of a GSRS score of ≥ 3 in 1 question for 1 day or a GSRS score of ≥ 2 in 1 question for 2 consecutive days, the subject will receive an alert through his/her eDiary to begin taking the randomized study treatment the same day. Any subject who does not reach the GSRS threshold during the DMF-GI Monitoring Period will be discontinued.

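### SAP 7.3.2 lists constipation and hard stools under both the diarrhea and the constipation dimension, so the diarrhea sub-score is mostly constipation and two of the 15 GSRS items belong to no dimension

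*Combined protocol and SAP*

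**What the plan says.** SAP 7.3.2 (GSRS score) describes a 15-item scale and states: "In addition, these 15 items can be grouped into 5 dimensions". It gives item counts of 3, 2, 4, 3 and 3 and names the items in each group. Two of the groups are "diarrhea syndrome (3 items, constipation, hard stools and urgency of defecation" and "constipation syndrome (3 items, constipation, hard stools and" feeling of incomplete evacuation (the last name follows a page break).

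The next sentence turns the lists into a scoring rule: "A dimension score is calculated as the mean of the items belonging to the specific syndrome".

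The same section defines the overall score without using the grouping: "The overall GSRS score is the mean of these 15 items, varying from 0 to 6". It bases the primary analysis on that overall score and gives the sub-scores a supporting role: "sensitivity analysis will be based on the 5 dimension score as appropriate".

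The SAP's list of tables plans results both overall and by dimension in Tables 15.1, 15.2 and 16 (average change, Day 1 to Day 10) and Table 18 (Day 1 to Week 10). Protocol 4.4 refers to 15 questions but neither names nor groups them, so nothing elsewhere in the documents corrects the list.

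**The concern.** A diarrhea score that averages constipation, hard stools and urgency does not measure what its label says. It shares two of its three items with the constipation score, so the two rows cannot be read as separate symptom groups. No item named for diarrhea appears in any of the five lists, although the Synopsis and Protocol 5.2 name diarrhea first among the GI events associated with DMF. A reader who turned to the by-dimension tables to ask whether montelukast helped diarrhea could be misled in either direction. The list matters because it is the only scoring rule given: a programmer working from the SAP alone would have no other source.

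**Working it through.** **Inputs.** All are from SAP 7.3.2.

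| Dimension | Stated count | Items named |
|---|---|---|
| Abdominal pain | 3 | abdominal pain; hunger pain; nausea |
| Reflux | 2 | heartburn; acid regurgitation |
| Indigestion | 4 | abdominal distension; increased flatulence; borborygmus; eructation |
| Diarrhea | 3 | **constipation**; **hard stools**; urgency of defecation |
| Constipation | 3 | **constipation**; **hard stools**; feeling of incomplete evacuation |

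**Step 1, the plan's own count.** Slots: 3 + 2 + 4 + 3 + 3 = 15. This matches the stated 15 items.

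**Step 2, distinct items.** Two names occur twice, so distinct items = 15 − 2 = 13. Items of the scale in no dimension = 15 − 13 = 2. Diarrhea items shared with the constipation list = 2 of 3.

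**Step 3, what the rule does to a single diary day.**
- Constipation = 6, hard stools = 6, all else 0: diarrhea score = 12/3 = 4.0, constipation score = 12/3 = 4.0, overall = 12/15 = 0.8.
- The two unlisted items = 6, all else 0: every dimension scores 0, overall = 12/15 = 0.8.

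The overall score is the same whatever the grouping.

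**Step 4, effect on a treatment difference.** Assume that the two unassigned items belong in the duplicated slots, that the difference is *e* on each of the three intended diarrhea items, and that it is *c* on constipation and on hard stools. The row as written shows (c + c + e)/3 = (2c + e)/3; with the slots corrected it shows (e + e + e)/3 = e. The documents give no values for *c* or *e*. For illustration, with e = −0.6:

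| c | Row as written | Share of e lost |
|---|---|---|
| −0.6 (c = e) | −0.60 | none |
| −0.3 (c = e/2) | −0.40 | one third |
| 0 | −0.20 | two thirds |

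If *c* has the opposite sign the loss is larger (c = −e/2 gives zero). If *c* exceeds *e* in size with the same sign, the row overstates the effect.

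**Step 5, overlap between the two sub-scores.** Assume equal item variances and a common inter-item correlation *r*. Of the 9 item pairs, 2 are the same item, so the correlation between the diarrhea and constipation scores is (2 + 7r)/(3 + 6r) as written, against 9r/(3 + 6r) with no shared items.

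| r | As written | No shared items |
|---|---|---|
| 0 | 0.67 | 0 |
| 0.3 | 0.85 | 0.56 |
| 0.5 | 0.92 | 0.75 |

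**Step 6, reach.** Four tables report by dimension. If each has one overall and five dimension row groups (the SAP gives titles, not shells), that is 4 × 6 = 24 row groups, of which the 4 diarrhea groups are wrong. None of the 4 overall groups is affected.

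**The case against.** The strongest objection is that the duplication may come from reading the PDF rather than from the SAP. The extracted text repeats phrases elsewhere: in SAP 3.1 the sentence on 59 subjects per arm loops back on itself, while Protocol 7.1 carries it intact, and Protocol 5.1.2 gives the T2-lesion result twice. Here two adjacent brackets open in the same way, and the second runs across a page break. Matching item counts prove little, because swapping one set of three names for another leaves the count right. This stands as a reason to check the source page first. It does not show that the list was misread: the sentence is whole and legible, and nothing in the documents contradicts it.

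The second objection is that almost nothing depends on the list. That is largely right. The sub-scores are sensitivity material, no objective or endpoint is specific to diarrhea, and the treatment trigger works question by question: "in 1 question for 2 consecutive days, the subject will receive an alert through his/her eDiary". Item-level data are collected as well (Protocol 4.4: "The 7 severities of each of the 15 questions of the GSRS have a number assigned"), so a wrong sub-score can be recomputed. A programmer who knows the instrument might also notice the slip. These points limit the severity; they do not make the written rule correct.

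The third objection is that the dilution figures use invented values of *c* and *e*. They do, and they show only how the error would act, not how large it would be in this trial.

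**Conclusion.** The list in SAP 7.3.2 is wrong as written. It claims to group 15 items but names 13, counts two of them twice, and makes two of the three diarrhea items constipation items. If it was programmed literally, the diarrhea rows in Tables 15.1, 15.2, 16 and 18 would be mislabelled and would overlap with the constipation rows.

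The severity is minor. Overall-score results, the primary endpoint, the listed secondary endpoints, the eDiary threshold and the sample size are untouched, and no data are lost. Confidence is medium, because the conclusion assumes that the source page reads as the extracted text does. The size of any distortion in a treatment difference cannot be stated from the documents.

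**What to change.** 1. Check the dimension list against the source SAP page.
2. If it reads as here, replace constipation and hard stools in the diarrhea list with the two eDiary questions that no dimension currently contains. The documents do not name these two, so they must be taken from the eDiary's 15 questions.
3. Confirm that the five lists then hold 3 + 2 + 4 + 3 + 3 = 15 distinct items, each in exactly one dimension.
4. Check that the dimension-score program behind Tables 15.1, 15.2, 16 and 18 does not use the printed list.

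The cost is a page check, a one-line SAP correction and a program check. Data collection, sample size and the primary and listed secondary analyses stay as they are.

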7.3.3 Analysis Methods-Primary endpoints

Proportion of subjects with a worsening in the severity of GI AEs, measured by the average change from Day 0 to Day 10 in GSRS score

The average change of the GSRS score from Day 0 (baseline) to Day 10 will be calculated as the sum of changes from baseline in GSRS score over the first 10 days divided by the total number of days with GSRS recorded. A positive average change of GSRS score from Day 0 to Day 10 means a patient has an overall worsened GI severity. A negative average change of GSRS score from Day 0 to Day 10 means an overall improved GI severity.

The proportion of subjects with worsening will be summarized by treatment and will be estimated from a weighted logistic regression model adjusted for age, weight and baseline GSRS score as continuous variables. Each patient included in this model will be assigned a weight defined as the proportion of days with GSRS score recorded. The weight is used to account for the missing data when patients do not report the GSRS score. The odds ratio (OR) for the Montelukast treatment group compared to placebo will be reported. The corresponding P-value from the likelihood ratio test of the null hypothesis that the OR = 1 will be given. Profile likelihood 95% profile likelihood confidence interval (CIs) will be given for the odds ratio.

SAS procedure "genmod" or SAS procedure "logistic" will be used to perform the primary analysis. Below is the example of SAS procedure genmod:

```
proc genmod data=ds1 descending;*assuming ds1 is the name of the data
set
    class trtpn;
    model worsec = trtpn weight age gsrsb/dist=bin link=logit lrci;
    weight pdays;
    lsmeans trtpn / pdiff cl;
    contrast "difference between treatments" trtpn -1 1;
run;
```

Depending on the GSRS, study treatment and/or the DMF compliance, sensitivity analysis may be performed among patients with a compliance rate from Day 0 to Day 10 above a certain threshold. A chi-squared test for the difference in the rate of worsening between the two treatment groups may also be performed.

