6 SAMPLE SIZE JUSTIFICATION

Assuming that 40% of the placebo subjects will be improving (by chance) without any intervention, a total sample size of 118 (dosed with randomized study treatment), 59 per treatment arm (after randomization), would provide approximately 80% power to detect a 30% difference between the treatment arm and placebo arm in proportion of subjects with any improvement in GI severity, as measured by the average change from Day 0 in GSRS score to Day 10. Power was estimated assuming a 15% early discontinuation rate.

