7 STATISTICAL ANALYSIS METHODS

The statistical software, SAS[®], will be used for all summaries and statistical analyses.

Summary statistics will be used throughout. For continuous endpoints, the summary statistics will generally include: the number of subjects with data, mean, standard deviation (SD), median, 25th and 75th percentile (Q1, Q3), minimum and maximum. For categorical endpoints, the summary statistics will generally include: number of patients randomized and dosed, the number of patients with data, and the number and percent of subjects with data in each category.

All statistical tests will be 2-sided with a type I error rate of 5%, unless otherwise specified.

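### The LS-means in SAP 7.3.3's example code are not the arms' worsening proportions; at the planned rates they would widen the 30-point difference by about 0 to 20 points, depending on an undocumented covariate strength

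*Combined protocol and SAP*

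**What the plan says.** The primary endpoint is a proportion: subjects whose average GSRS change over Days 1 to 10 is positive. On its estimation, SAP 7.3.3 says: "The proportion of subjects with worsening will be summarized by treatment and will be estimated from a weighted logistic regression model". The covariates are age, weight and baseline (Day 0) GSRS, all continuous. Each subject is weighted by the share of days with a diary score.

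The example PROC GENMOD code contains one line that produces per-arm estimates: "lsmeans trtpn / pdiff cl". It has no ILINK option, sets no covariate values and does no averaging over subjects. The contrast to be reported is the odds ratio, with a likelihood ratio P-value and a profile likelihood 95% CI. A chi-squared test of the rate difference is optional.

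SAP section 6 sizes the trial on a difference in proportions. It begins: "Assuming that 40% of the placebo subjects will be improving (by chance) without any intervention". The planned number, it says, "would provide approximately 80% power to detect a 30% difference between the treatment arm and placebo arm in proportion of subjects" with any improvement.

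**The concern.** LSMEANS evaluates the linear predictor with continuous covariates at their means. In a logistic model the inverse logit of an average is not the average of the inverse logits. A back-transformed LS-mean is therefore the risk of one hypothetical subject with mean age, mean weight and mean Day 0 GSRS, and it differs from the arm's average risk whenever a covariate is prognostic.

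Day 0 GSRS is likely to be prognostic here. It is a covariate and is also the value subtracted to define worsening, so some dependence is built in through regression to the mean.

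At stake is the reported size of the primary effect. A programmer who follows the example and adds a back-transformation will tabulate proportions that disagree with the raw percentages. Their difference does not estimate the quantity on which the trial was sized.

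**Working it through.** **Inputs.** From the documents: 40% improving on placebo, a 30-point difference, about 80% power, 118 dosed (59 per arm) and 15% early discontinuation (SAP 6); two-sided 5% (SAP 7); 1:1 allocation (protocol 9.2). Assumed: exact-zero average changes are ignored, so 40%/70% improving is read as 60%/30% worsening. Also assumed: σ, the SD of the covariate part of the linear predictor on the logit scale, for which the documents give no figure.

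**1. The plan's own figure.** With p̄ = 0.55,

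n = [1.960·√(2·0.55·0.45) + 0.842·√(0.4·0.6 + 0.7·0.3)]² / 0.30² = 41.97, so 42 per arm.

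With continuity correction, n′ = (n/4)·[1 + √(1 + 4/(0.30·n))]² = 48.4, so 49. Dividing by 0.85 gives 57.6, so 58 per arm and 116 in total, against the stated 118. The plan's figure is reproduced, and its target quantity is a difference in crude proportions.

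**2. LS-mean against arm proportion.** Let the covariate part be σZ with Z standard normal. For an arm with true worsening rate p, solve E[expit(a + σZ)] = p for a. The back-transformed LS-mean is expit(a). At σ = 1, a = 0.490 for placebo and −1.018 for montelukast, giving 62.0% and 26.5%.

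| σ | OR per SD | LS-mean, placebo | LS-mean, montelukast | Difference | Excess over 30 |
|---|---|---|---|---|---|
| 0 | 1.0 | 60.0 | 30.0 | 30.0 | 0 |
| 0.5 | 1.65 | 60.6 | 29.0 | 31.6 | +1.6 |
| 1.0 | 2.72 | 62.0 | 26.5 | 35.5 | +5.5 |
| 1.5 | 4.48 | 63.9 | 23.4 | 40.6 | +10.6 |
| 2.0 | 7.39 | 66.1 | 20.0 | 46.1 | +16.1 |
| 2.4 | 11.0 | 67.9 | 17.4 | 50.5 | +20.5 |

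With right-skewed (gamma) covariates and σ from 0.5 to 2.5, the excess runs from +1.2 to +16.9.

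**3. What σ might be.** Suppose a subject's level is N(0,1), Day 0 is the level plus daily noise, and the 10-day mean is the level plus a shift plus noise/√10. Shifts are set to give 60%/30% worsening, and worsening is regressed on arm and Day 0 (200,000 per arm).

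| Noise variance ÷ between-subject variance | LS-mean proportions | Difference | Standardized proportions | Conditional OR |
|---|---|---|---|---|
| 0.1 | 60.5 / 29.0 | 31.5 | 60 / 30 | 0.27 |
| 0.25 | 61.3 / 27.9 | 33.4 | 60 / 30 | 0.24 |
| 0.5 | 62.4 / 25.9 | 36.5 | 60 / 30 | 0.21 |
| 1 | 63.9 / 22.9 | 41.0 | 60 / 30 | 0.17 |
| 2 | 66.8 / 19.0 | 47.9 | 60 / 30 | 0.12 |

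The marginal OR is (0.30/0.70)/(0.60/0.40) = 0.29 throughout. If the daily noise is itself correlated from day to day (AR(1), 0.8), ratios of 0.5, 1 and 2 give excesses of only +3.3, +5.3 and +7.2.

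**4. Direction at other rates.** The same calculation as step 2, for σ from 1 to 2:

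| True rates | True difference | LS-mean difference |
|---|---|---|
| 40% / 20% | 20 | 21.9 to 24.2 |
| 30% / 15% | 15 | 15.1 to 14.0 |
| 30% / 10% | 20 | 19.4 to 16.9 |

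Widening is assured only when the arms lie on opposite sides of 50%. When both rates are low, the sign can reverse.

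**5. Realistic sizes.** Weighted logistic fits (500 per setting, true rates 60%/30%, assumed diary weights averaging about 0.9) at σ = 1, 1.5 and 2 gave LS-mean differences of 36.9, 41.5 and 46.2 points at N = 118, and 37.9, 42.7 and 48.9 at N = 60. Standardized differences were 30.4, 29.9 and 29.2, and 30.6, 30.2 and 30.0.

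**The case against.** Five points weigh against a strong version of this.

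- **The SAP text does not name LS-means.** The code is labelled an example, PROC LOGISTIC is an allowed alternative, and without ILINK the line returns log-odds. A reader might infer that the SAP commits to LS-mean proportions, but it does not. It leaves the estimator open, and its only illustration points to LS-means. This stands, and it is a reason to specify the step.
- **Raw percentages are planned.** SAP 7.3.3 summarizes the proportion by treatment, and SAP 7 gives counts and percentages for categorical endpoints. The raw difference can be set against the planned 30 points. This stands.
- **The size is not in the documents.** A reader might infer from the wider rows above an overstatement of at least 6 points. Nothing in the plan supports a floor: small day-to-day noise gives 2 to 3 points, and a covariate with no prognostic value gives none.
- **Inference is untouched.** The odds ratio, its interval and the likelihood ratio test do not use LS-means. A reader might infer that the primary test is biased, or that a conditional OR of 0.17 beside a marginal 0.29 is an error. Neither follows: the gap is non-collapsibility, and a conditional OR is a legitimate effect measure.
- **Precision is low.** SAP 5 closes enrolment at about 60 dosed. With 30 per arm, the standard error of the difference is √(0.24/30 + 0.21/30) = 12.2 points, larger than most plausible values of this bias. That is true, but a systematic shift in the reported primary proportions is still worth removing when removal is nearly free.

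**Conclusion.** The point holds in a limited form. Back-transformed LS-means from the example code would not estimate the arms' proportions. At 60%/30% worsening they would widen the 30-point difference by about 0 to 20 points, which corresponds to σ from 0 to about 2.4. That range is an assumption, because the documents say nothing about covariate strength. It also rests on reading 40%/70% improving as 60%/30% worsening. Confidence is high that LS-means and arm proportions differ when a covariate is prognostic. It is not high on the size, and the direction is settled only for rates on either side of 50%.

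The damage is confined to the model-based proportions and any difference read from them. The remaining gap is that no adjusted difference in proportions with a CI is defined, although SAP 6 sizes the trial on a difference. This should be fixed, but it does not threaten the primary test.

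**What to change.** In SAP 7.3.3, replace the LSMEANS step with standardization:

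- From the fitted weighted model, predict each mITT subject's probability of worsening with treatment set to montelukast and again with it set to placebo, keeping the subject's own covariates.
- Average each set of predictions over the whole mITT population.
- Report the two standardized proportions and their difference with a 95% CI (delta method or bootstrap), beside the crude proportions, the odds ratio with its profile likelihood CI, and the likelihood ratio P-value.

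The cost is SAP wording and a few lines of code. No new data are needed and the primary test does not change. At the planned rates the reported model-based difference becomes less favourable to montelukast than the back-transformed LS-means would suggest.

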12. WITHDRAWAL OF SUBJECTS FROM STUDY TREATMENT **AND/OR THE STUDY**

A subject *must* permanently discontinue study treatment and be withdrawn from the study for any of the following reasons:

- Failure to meet the required eDiary compliance criteria (\geq 75%) in the 14 days prior to randomization.
- Failure to meet the GSRS score criteria during the DMF-GI Monitoring Period. •
- The subject experiences a medical emergency that necessitates permanent discontinuation of study treatment.
- The subject uses prohibited concomitant medications (as outlined in Sections 1 and 10.3.1).
- The subject withdraws consent.

Protocol 109MS414

- At the discretion of the Investigator for medical reasons or for noncompliance.
- The subject has a concurrent illness or injury, or abuses alcohol or drugs to the extent that, in the judgment of the Investigator and/or Sponsor, it would affect assessments of clinical status to a significant degree.

The reason for discontinuation of study treatment and withdrawal from the study must be recorded in the subject's CRF.

Subjects who discontinue study treatment will be withdrawn from the study. Whenever possible, subjects who prematurely discontinue study treatment should complete an ET Visit (undergoing the same assessments as the Week 10 Visit).

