16.4.3. Primary Endpoint Analysis

Change from Day 0 to Day 10 in GSRS rating will be computed. The proportion of subjects with worsening in GI AEs, defined as increases in GSRS ratings, will be estimated to obtain the rate of worsening in the 2 arms. The difference in the rate of worsening in GI AEs will be analyzed using a chi-square test and the logistic regression model, adjusting for covariates and confounding factors.

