5 INTERIM ANALYSIS

No interim analysis will be performed. The study will be stopped for administrative reasons. Enrollment will be closed when approximately 60 patients are randomized and dosed up to Day 10. Enrolled patients will be followed until they complete the safety follow up visit. Results will be reviewed at the group level when these patients complete the study up to Day 10, and at the subject level when these patients complete the whole study.

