7.1 Analysis population

7.1.1 Modified ITT population

The modified intent-to-treat (modified ITT) population consists of all patients who were randomized, received at least one dose of DMF treatment, received at least one dose of study treatment (Montelukast or placebo) on/after the first DMF dose date, and had at least one GSRS score measurement during the Day 1 - Day 10 period.

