GSRS score compliance rate will be summarized in the modified ITT population. GSRS score compliance rate will be defined as the total number of days when the GSRS score is recorded divided by the total number of days when the GSRS score is expected to be recorded. GSRS score compliance will be summarized in each of the following periods:

- From Day 0 to Day 10
- Form Day 0 to Week 10

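### The primary logistic model weights each subject by diary completeness, which makes the trial count as smaller than it is and does not correct for missing days

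*Combined protocol and SAP*

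**What the plan says.** Protocol section 16.4.3 says the difference in worsening rates "will be analyzed using a chi-square test and the logistic regression model", adjusted for covariates. It mentions no weight.

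SAP section 7.3.3 makes a weighted logistic regression the primary analysis, adjusted for age, body weight and baseline GSRS: "Each patient included in this model will be assigned a weight defined as the proportion of days with GSRS score recorded". The reason given is: "The weight is used to account for the missing data when patients do not report the GSRS score". The example code is PROC GENMOD with `dist=bin link=logit lrci` and `weight pdays`. It contains no normalisation step, scale option or robust variance. PROC LOGISTIC is allowed as an alternative, again with no mention of normalisation. The p-value comes from the likelihood ratio test and the interval from the profile likelihood. The chi-square test is now optional: "A chi-squared test for the difference in the rate of worsening between the two treatment groups may also be performed".

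Four other provisions bear on the weight:

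- SAP 7.1.1 admits any dosed subject who "had at least one GSRS score measurement during the Day 1 - Day 10 period", so the weight can be as low as 0.1 if taken over ten days.
- SAP 7.2.7 defines a similar quantity, diary compliance, as days recorded "divided by the total number of days when the GSRS score is expected to be recorded". SAP 7.3.3 does not say whether `pdays` uses that denominator.
- Protocol section 12 states: "Subjects who discontinue study treatment will be withdrawn from the study".
- SAP section 5 states: "Enrollment will be closed when approximately 60 patients are randomized and dosed up to Day 10". The planned number was 118.

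**The concern.** Each subject contributes one binary outcome. In a binomial model with dispersion fixed at 1, a weight multiplies that subject's log-likelihood, so a subject with 8 of 10 diaries counts as 0.8 of a subject. The test statistic shrinks and the interval widens, although the number of independent outcomes has not changed.

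The weight also fails its stated purpose. The outcome already averages over recorded days only. Giving less influence to subjects with more missing days tells us nothing about those days, and gives least say to those with the most missing data. Someone who worsens, stops treatment and is withdrawn may be counted least of all.

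At stake are the precision and power of the primary comparison in a trial closed at about half its planned size, and the accuracy of the model-based worsening proportions. As the SAP stands, no unweighted test of the primary endpoint is committed. Planned Table 14 does not fill that gap, because it keeps only subjects with at least 80% diary compliance and minimum dose counts.

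**Working it through.** **Inputs from the documents.** Two-sided alpha 0.05 (SAP 7); 40% improving on placebo, a 30-point difference, 15% early discontinuation and 59 per arm (SAP 6); 1:1 allocation (protocol 9.2); about 60 dosed at closure (SAP 5), taken as 30 per arm. Ignoring ties, worsening is 60% versus 30%.

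**Step 1: the plan's own figure.** An ordinary unweighted comparison of 40% with 70% at 80% power needs 42 per arm, or 49 with continuity correction. Then 49/0.85 = 57.6, or 58 per arm and 116 in total, close to the stated 118. The sizing is consistent with an unweighted test and makes no allowance for the weight.

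**Step 2: uniform completion, large-sample formula.** With a constant weight m, the likelihood ratio statistic is multiplied by m. The actual size is P(chi-square on 1 df > 3.841/m) and the interval is 1/√m times as wide.

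| m | Size of the nominal 5% test | Interval width factor | 60 subjects count as |
|---|---|---|---|
| 0.95 | 4.4% | 1.026 | 57 |
| 0.90 | 3.9% | 1.054 | 54 |
| 0.80 | 2.8% | 1.118 | 48 |

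**Step 3: simulation with unequal weights.** Assumed: 90% daily completion, 15% stopping uniformly on Days 2-5, three non-prognostic covariates, 14,000 trials per cell. Calibrated power uses the simulated null 95th percentile as the critical value. Monte Carlo error is about 0.2 points for type I error and 0.3-0.5 for power. With `pdays` taken over ten days, the mean weight is 0.81 and the interval is 12% wider:

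| Per arm | Type I error, unweighted / weighted | Nominal power, unweighted / weighted | Calibrated power, unweighted / weighted |
|---|---|---|---|
| 30 | 5.9% / 4.3% | 66.3% / 58.4% | 63.7% / 60.5% |
| 59 | 5.5% / 4.0% | 91.9% / 87.0% | 91.1% / 88.9% |

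The unweighted chi-square test in the same runs has type I error 4.7% and 5.0%, and power 66.5% and 92.3%, at 30 and 59 per arm.

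Other settings, as power lost at 30 and 59 per arm:

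- `pdays` over days until withdrawal (mean weight 0.90): nominal 4 and 2 points; calibrated under 1 point.
- 95% completion, 5% stopping: nominal 3.5 and 1.7 points; calibrated 2.0 and 0.9.
- 98% completion, no stopping: 1 point or less.

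**Step 4: would normalising be enough?** With weights rescaled to mean 1 and the model-based likelihood ratio test, type I error is 6.9% at 30 per arm and 6.7% at 59. With a robust variance it is 4.4% and 4.9%.

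**Step 5: outcome-related stopping.** Suppose a share s of an arm worsens and stops at Day 3. Over ten days these subjects have weight 3/10 = 0.3; over days until withdrawal they would have 3/3 = 1. Under the ten-day reading, and giving everyone else weight 1, the weighted worsening rate is (p − s + 0.3s)/(1 − s + 0.3s). With true rates of 60% and 30% (OR 0.286):

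- s = 5% on placebo only: (0.55 + 0.015)/(0.95 + 0.015) = 58.5%, OR 0.303. Protocol 5.2 gives 5% as the upper figure for GI discontinuation on DMF.
- s = 5% in each arm: 58.5% and 27.5%, OR 0.268.
- s = 10% and 5%, the same share of worseners in each arm: 57.0% and 27.5%, OR 0.286.

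The proportions are distorted in each affected arm. The OR moves only when the share of worseners who stop differs between arms, and it can move either way.

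**The case against.** The strongest reply is about size. The formula sizes in Step 2 are asymptotic. In a separate simulation at 30 per arm (null worsening rate 45%, 8,000 trials per cell), 90% completion without stopping gave type I error of 4.9% weighted against 5.9% unweighted. The weighted test was therefore near nominal and the unweighted likelihood ratio test was the liberal one. Much of the nominal power loss comes from comparing a slightly liberal test with a conservative one; calibrated, it is 2 to 3 points even in the severe setting. That setting is assumed: the SAP gives no timing for its 15% discontinuation, earlier GI discontinuation was at most 5%, and entry requires at least 75% diary compliance. The OR shifts in Step 5 are about 0.1 of a standard error (log-OR standard error about 0.55 at 30 per arm). All of this stands, and it limits the severity.

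Other replies carry less weight:

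- **Precision.** Down-weighting a one-day diary can be defended because its classification is noisier. In a day-level simulation with short diaries noisier (assumed within-subject correlation 0.5), the weight still lost power at 30 per arm: nominal 64.0% to 56.7%, calibrated 61.7% to 58.8%.
- **The denominator.** Ten days is the natural reading of SAP 7.3.3, but it is not stated, and the choice moves the mean weight from 0.81 to 0.90.
- **The MMRM in SAP 7.3.4.** It is committed and does use incomplete diaries, but it tests the continuous change, not the binary primary endpoint.
- **Example code.** The absence of normalisation is read from code labelled an example; nothing in the SAP text says otherwise.

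**Conclusion.** The concern holds and should be fixed. As written, the primary test and interval understate the information in the trial whenever diary days are missing, and the weight does not do what the SAP says it does. The scale error is conservative: it threatens power and interval width, not false positives. Under 90% completion and 15% early stopping the loss at 30 per arm is about 8 points of nominal power, or about 3 points calibrated. It is 1 point or less at 98% completion with no stopping. These figures rest on assumed completion, stopping times and worsening rates. Any bias in the OR also requires outcome-related stopping that differs between arms. The mechanism and the departure from the protocol's committed chi-square test do not depend on those assumptions. The scale problem does not extend to the weighted ANCOVA in SAP 7.3.4, which estimates its own residual variance.

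**What to change.** Delete the `weight pdays` statement and its explanatory sentences, so that each modified ITT subject counts once in the primary logistic model. Make the unweighted chi-square test a committed analysis, as in protocol 16.4.3. Pre-specify one supportive analysis that counts discontinuation for GI events before Day 10 as worsening; reasons for discontinuation are already collected.

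If the weight is kept, state its denominator, normalise it and use a robust variance. Normalising alone is not enough.

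The cost is one line of code and two or three SAP sentences, with no new data. There are two downsides. Subjects with few diary days are classified more noisily at full weight. The unweighted likelihood ratio test is also slightly liberal at 30 per arm (5.9%), which is a further reason to commit to the chi-square test (4.7%).
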